	A female participant is eligible to participate if she is either:				
	 Not a WOCBP as defined in Appendix 7 (proper documentation must be provided to confirm non-WOCBP status) 				
	OR				
	 A WOCBP who is not pregnant (ie, has a negative serum pregnancy test result at the Screening visit and has a negative serum or urine pregnancy test result at the Baseline visit), and agrees to follow the contraceptive guidance in Appendix 7 during the intervention period 				
5.	Informed Consent				
5.01	Capable of giving signed informed consent as described in Appendix 1, which includes compliance with the requirements and restrictions listed in the ICF and in this protocol				
5.02	Written informed consent from the participant has been obtained prior to any study-related procedures				
6.	Other				
6.01	Able, as assessed by the investigator, and willing to follow study instructions and likely to complete all required study visits				

5.2.2. Exclusion Criteria for Stage 2

Participants are excluded from Stage 2 of the study if any of the following criteria apply:

1.	Medical Conditions			
1.01	Current diagnosis of glaucoma or ocular hypertension; evidence of glaucoma or mean (or median) intraocular pressure > 21 mm Hg determined by Goldmann applanation tonometry, in either eye at the Screening visit			
1.02	History or presence of any ocular disorder or condition (other than DED) in either eye that would, in the opinion of the investigator, likely interfere with the interpretation of the study results or participant safety, such as: significant corneal or conjunctival scarring; pterygium or nodular pinguecula; conjunctivitis, or inflammation not associated with DED; anterior (epithelial) basement membrane corneal dystrophy or other clinically significant corneal dystrophy or degeneration; evidence of keratoconus; etc. (Note: Blepharitis and/or Meibomian gland disease not requiring treatment are allowed.)			
1.03	Diagnosis of recurrent, ongoing, or active ocular infection including, but not limited to herpes simplex or zoster, vaccinia, varicella, tuberculosis of the eye, acanthamoeba, or fungal disease			
1.04	History of ocular surgery within 12 months prior to the Screening visit, including punctal cautery, corneal refractive, or anterior segment surgeries that affect corneal sensitivity (eg, cataract surgery or any surgery involving limbal or corneal incision)			
1.05	Have had a corneal transplant in either or both eyes			

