9.8 Biomicroscopy and Ophthalmoscopy

Biomicroscopy will be performed in each eye at each visit, by slit-lamp examination, without pupil dilation, including but not limited to lids/lashes, conjunctiva, cornea, and

anterior chamber. Observations for the examination will be graded on a 5-point scale (0=none, 0.5=trace, 1=mild, 2=moderate, 3=severe) except for a) the anterior chamber cells: 0=0 cells, +0.5=1-5 cells, +1=6-15 cells, +2=16-25 cells, +3=26-50 cells, and +4=> 50 cells; and b) flare: 0=none, +1=faint, +2=moderate, +3= marked and +4=intense).

will be summarized using descriptive statistics at all post-baseline visits and pre-/post-CAE when applicable. For Pre-CAE change from baseline, the Day 1 Pre-CAE value prior to the administration of the first administration of study intervention will be used as baseline. For Post-CAE change from baseline, the Day 1 Post-CAE value prior to the administration of the first administration of study intervention will be used as baseline.

The number of participants with biomicroscopy findings of ≥ 2-grade severity increase from baseline will be generated for MedDRA preferred terms recorded on the Ocular Biomicroscopic Exam eCRFs at each post-baseline visit by study intervention for each eye. For findings under other pathology which are not associated with a severity grade, a status change from absent to present will be treated as a 2-grade increase in the analysis. At least 2-grade increase in severity from baseline is defined as a change from no finding to 2 and above, from 0.5 to 2 and above, or from 1 to 3 and above from baseline at any of the follow-up visits. The number and percentage of participants with clinically significant biomicroscopy findings (at least 2-grade increase in severity from baseline) will be tabulated by finding category, and study intervention group.

The ophthalmoscopy findings will be summarized similarly.

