5.6.3.8. Biomicroscopy

Slit-lamp biomicroscopy exam will be performed in each eye.

The number of participants with biomicroscopy findings of any severity increase from baseline at one or more visits will be generated for each MedDRA preferred terms by cohort and study

Safety Statistical Analysis Plan

2012-201-005 [Stage 1]

intervention group for each eye. For findings under "other pathology" which are not associated with a severity grade, a status change from absent to present will be treated as an increase of severity in the analysis.

Table 5-14 Biomicroscopy

Parameter	Description	Timing	Methodology
Biomicroscopy	Any severity increase from baseline for each eye	Treatment period	Categorical descriptives

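### The Stage 2 list of 2-grade slit-lamp increases stops at baseline grade 1, so it misses a 2-to-4 rise in anterior chamber cells or flare, and the tables built on it omit low-grade new cells and flare

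*SAP*

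**What the plan says.** Slit-lamp biomicroscopy is one of the assessments under the primary safety objective of Stage 2 (protocol 3.2; Stage 2 SAP Table 1 and 3.1).

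Stage 2 SAP 9.8 grades most slit-lamp observations 0, 0.5, 1, 2 or 3. Two have their own scales. Anterior chamber cells are graded "0=0 cells, +0.5=1-5 cells, +1=6-15 cells, +2=16-25 cells, +3=26-50 cells", with a further grade +4 above 50 cells. For flare the scale is "flare: 0=none, +1=faint, +2=moderate, +3= marked and +4=intense". Protocol Tables 8-9 and 8-10 give the same grades.

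Section 9.8 builds two summaries on a 2-grade increase: a count per preferred term by visit, arm and eye, and a table in which "clinically significant biomicroscopy findings (at least 2-grade increase in severity from baseline) will be tabulated by finding category" and arm. The increase is defined as "a change from no finding to 2 and above, from 0.5 to 2 and above, or from 1 to 3 and above". No separate definition is given for cells or flare. For ungraded findings recorded as other pathology, "a status change from absent to present will be treated as a 2-grade increase in the analysis".

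Protocol 9.4.2.7, headed Biomicroscopy and applying to each stage, sets a 2-grade threshold without listing transitions; its sentence speaks of ophthalmoscopy findings. Stage 1 SAP 5.6.3.8 instead reports "The number of participants with biomicroscopy findings of any severity increase from baseline at one or more visits". Stage 2 SAP Appendix E records one change from the protocol, the dropping of between-group tests on safety data, and does not mention the slit-lamp rule.

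**The concern.** The list names baselines 0, 0.5 and 1 and then stops. On a scale that ends at 3 nothing is lost, because an eye at grade 2 can rise by only one grade. On a scale that ends at 4, an eye at grade 2 can rise by two, and the list has no entry for it.

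The list also decides what is seen from a clean eye, the expected starting point. Protocol 5.2.2, criterion 1.02, names "conjunctivitis, or inflammation not associated with DED" among its examples of ocular conditions that exclude a participant when the investigator thinks they would interfere, so most eyes should enter at grade 0 for cells and flare. From there the lowest qualifying result is grade 2, that is 16 or more cells or moderate flare.

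Cells and flare are the graded slit-lamp signs of inflammation in the anterior chamber. Protocol 2.2.1.4 reports no clinical experience with AGN-242428 as an eye drop, and 2.2.2.4 none with AGN-231868 by any route. A by-arm view of low-grade new cells and flare would therefore be useful, and the 2-grade tables cannot give it.

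**Working it through.** The documents state no figure for this point, so the check lists every possible worsening (baseline grade to any higher grade) on each scale in Stage 2 SAP 9.8 and applies the rule as written.

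**Possible worsenings.** A scale with k levels has k(k − 1)/2.
- Lids, conjunctiva, cornea (0, 0.5, 1, 2, 3): 5 × 4 / 2 = 10.
- Cells (0, 0.5, 1, 2, 3, 4): 6 × 5 / 2 = 15.
- Flare (0, 1, 2, 3, 4): 5 × 4 / 2 = 10.

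**Counted by the SAP list.**
- Lids, conjunctiva, cornea: 2 from 0, 2 from 0.5, 1 from 1, total 5.
- Cells: 3 from 0, 3 from 0.5, 2 from 1, total 8.
- Flare: 3 from 0, 2 from 1, total 5.

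**Comparison with three ways of counting two grades.**

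| Reading | Lids, conjunctiva, cornea | Cells | Flare |
|---|---|---|---|
| SAP list | 5 | 8 | 5 |
| Numeric difference of 2 or more | 4 (drops 0.5→2) | 8 (drops 0.5→2, adds 2→4) | 6 (adds 2→4) |
| Two or more steps on the scale | 6 (adds 0→1) | 10 (adds 0→1 and 2→4) | 6 (adds 2→4) |
| Whole grades, trace grouped with none | 5 (same as list) | 9 (adds 2→4) | 6 (adds 2→4) |

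The last reading reproduces the list exactly on the 0–3 scales and differs from it on cells and flare only by 2→4. All three readings count 2→4, and the list does not.

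**From a grade 0 eye.**
- Cells can worsen to 0.5, 1, 2, 3 or 4. Two of the five (0.5 and 1, so 1 to 15 cells) are not counted.
- Flare can worsen to 1, 2, 3 or 4. One of the four (+1) is not counted.

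**Which of these depend on the counting convention.**
- Cells 0→0.5: one step, numeric difference 0.5. Below two grades on every reading.
- Flare 0→1: one step, numeric difference 1. Below two grades on every reading.
- Cells 0→1: two steps, but a numeric difference of 1 and one whole grade. Only this one turns on the convention.

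The absent-to-present provision does not bring these in, because it covers ungraded findings and both cells and flare are graded.

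**The case against.** The strongest reply is that the threshold is the protocol's. Section 9.4.2.7 sets two grades, and the Stage 2 SAP keeps it. A reader might infer from the Stage 1 rule, which counts any increase, that Stage 2 wrongly loosened the standard. The documents do not support that: Stage 1 is the stage that departs from the protocol's threshold. The stages also have separate SAPs, and no pooling of slit-lamp data is planned, so the two tables need not match.

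A reader might also infer that the list contradicts its own label, since it counts 0.5 to 2 but not 0 to 1. It is coherent if trace is grouped with none, as the table above shows. The SAP does not state that convention, but nothing in it rules the convention out.

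A third tempting inference is that low-grade cells and flare would go unreported. That goes too far:
- Protocol Appendix 3 makes abnormal safety assessments adverse events when the investigator judges them clinically significant, and SAP 9.2.2 and 9.2.3 summarise ocular events by arm.
- Tables and listings are specified in a separate document (SAP 1.0).
- Section 9.8 has a sentence on descriptive statistics whose subject is missing from the public text; it may or may not cover these grades.

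All of this stands. It leaves two things. The adverse-event route rests on investigator judgment and is no substitute for a tabulation of every graded eye. And none of it explains the missing 2-to-4 transition.

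**Conclusion.** The 2-to-4 gap for cells and flare is wrong as written: it is a rise of two grades on every reading, and the list omits it. Its practical reach is probably small, because criterion 1.02 should keep most eyes with grade 2 cells or flare out of the study.

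The rest is a cheap improvement. From a grade 0 eye, 2 of 5 cell worsenings and 1 of 4 flare worsenings do not reach the 2-grade tables. Showing new +0.5 cells and new +1 flare would add a safety display beyond the protocol's threshold; it would not correct an error. Cells 0 to +1 depends on an unstated counting convention.

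A reader might infer that a zero in the clinically significant row limits how often the drops cause any new cells or flare. It does not: the row counts a different, larger change. The documents give no rate for low-grade cells or flare, so the number of participants affected cannot be stated. The conclusion assumes that the list is exhaustive and that, with no separate rule given, it applies to cells and flare.

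**What to change.** In Stage 2 SAP 9.8:
- Keep the 2-grade rule as it stands for lids, conjunctiva and cornea.
- For anterior chamber cells and flare, add 2 to 4 to the qualifying transitions.
- Add two rows, by visit, eye and arm: participants whose eye was grade 0 at baseline and is +1 or more afterwards, one row for cells and one for flare.
- List any new +0.5 cells.

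The cells row shows the 0 to +1 change whichever way grades are counted, so that convention need not be settled for these findings to be seen.

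The cost is a sentence, two table rows and a short listing, from grades the study already collects. The drawback is that an occasional misgraded faint finding will be counted; the two vehicle arms put that in context.

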9.9 Safety Subgroup Analyses (if applicable)

No safety subgroup analyses are planned.

10.0 Interim Analyses

An interim database lock occurred after completion of Stage 1, and the unmasking and data analyses were performed. This doesn't affect masking of Stage 2. At the end of study, the final database lock will occur.

11.0 Version History

Table 4.SAP Version History Summary

Version	Date	Summary
1.0	07 December 2021	Original version

12.0 Appendices

AGN-242428 and AGN-231868 2012-201-005 – Statistical Analysis Plan (Stage 2) Version 1.0 – 07 December 2021

Appendix A. Protocol Deviations

According to ICH E3 2012 guideline, only important protocol deviations will be reported in CSR. The number and percentage of randomized participants with important protocol deviations will be summarized overall and by study intervention group for participants reported by protocol deviation categories:

- Participants who entered the study even though they did not satisfy the entry criteria
- Participants with inclusion criteria not met, overall and by inclusion criteria
- Participants with exclusion criteria met, overall and by exclusion criteria
- Participants developed withdrawal criteria during the study but were not withdrawn
- Participants received wrong treatment or incorrect dose of study treatment
- Participants took prohibited concomitant medication

Appendix B. Definition of Adverse Events of Special Interest

The following adverse events of special interest (AESI) (serious or nonserious) are defined in the protocol and will be summarized by PT terms listed in Table 5:

- AST and/or ALT increased to \geq 5 ULN
- AST and/or ALT increased to ≥ 3 × ULN AND total bilirubin increased to ≥ 2 × ULN. Typically, all analytes will be obtained from the same sample, but they may come from multiple samples taken within a 24-hour period.
- AST and/or ALT increased to ≥ 3 × ULN with symptoms believed to be related to liver injury (e.g., fatigue, nausea, vomiting, right upper quadrant pain or tenderness or jaundice) or hypersensitivity (such as fever, rash, or eosinophilia > 5%)
- Potential Hy's Law cases:
 - o ALT and/or AST \geq 3 × ULN AND
 - \circ TBL $\geq 2 \times$ ULN AND
 - \circ Alkaline phosphatase $< 2 \times ULN$

Table 5. List of Preferred Terms for Adverse Events of Special Interest

Preferred Term (PT)	PT Code
Aspartate aminotransferase increased	10003481
Alanine aminotransferase increased	10001551
Blood bilirubin increased	10005364
Blood alkaline phosphatase increased	10059570

Appendix C. Potentially Clinically Significant Criteria for Safety Endpoints

The potentially clinically significant criteria for clinical laboratory parameters, vital signs and ECG parameters are provided in the following sections.

Table 6. Potentially Clinically Significant Criteria for Clinical Laboratory Parameters

Laboratory Group	Parameter	SI Unit	PCS Low Limit	PCS High Limit
Hematology	Eosinophils absolute cell count	10 ⁹ /L	_	> 1.5 × ULN
	Hematocrit	%	< 0.8 × LLN	$\geq 1.2 \times ULN$
	Hemoglobin	g/L	< 0.8 × LLN	$\geq 1.2 \times ULN$
	Lymphocytes absolute cell count	10 ⁹ /L	< 0.8 × LLN	> 1.2 × ULN
	Neutrophils absolute cell count	10 ⁹ /L	< 0.6 × LLN	> 1.6 × ULN
	Platelet count (thrombocytes)	10 ⁹ /L	< 0.5 × LLN	> 1.5 × ULN
	Red blood cell count	$10^{12}/L$	< 0.8 × LLN	> 1.2 × ULN
	White blood cell count	10 ⁹ /L	< 0.7 × LLN	> 1.8 × ULN
Chemistry	Alanine aminotransferase	U/L		> 3 × ULN
	Albumin	g/L	< 0.9 × LLN	> 1.1 × ULN
	Alkaline phosphatase	U/L		> 3 × ULN
	Aspartate aminotransferase	U/L		> 3 × ULN
	Bilirubin, total	μmol/L	_	> 1.5 × ULN
	Blood urea nitrogen	mmol/L	_	> 1.3 × ULN
	Calcium	mmol/L	< 0.9 × LLN	> 1.1 × ULN
	Cholesterol, total	mmol/L	_	> 1.2 × ULN
	Creatinine	μmol/L	_	> 1.8 × ULN
	Glucose, fasting	mmol/L	< 0.8 × LLN	> 1.2 × ULN
	Glucose, nonfasting	mmol/L	< 0.8 × LLN	> 1.4 × ULN
	Phosphorus	mmol/L	< 0.8 × LLN	> 1.2 × ULN
	Potassium	mmol/L	< 0.9 × LLN	> 1.1 × ULN
	Protein, total	g/L	< 0.9 × LLN	> 1.1 × ULN
	Sodium	mmol/L	< 0.9 × LLN	> 1.1 × ULN
	Uric acid (urate)	μmol/L		> 1.2 × ULN

Laboratory Group	Parameter	SI Unit	PCS Low Limit	PCS High Limit
Urinalysis	Glucose	μmol/L		≥ 0.015
	Glucose (alternate units)	_		≥ 2+
	рН	_	< 0.9 × LLN	> 1.1 × ULN
	Protein	g/L		≥ 1.0
	Protein (alternate units)	_		≥ 2+
	Specific gravity	_	_	> 1.1 × ULN

LLN = lower limit of normal (value provided by the laboratory); PCS = potentially clinically significant; SI = *Le Système International d'Unités* (International System of Units); ULN = upper limit of normal (value provided by the laboratory)

Table 7. Potentially Clinically Significant Criteria for Vital Signs Parameters

			PCS Criteria	
Parameter	Unit	PCS Category	Actual Value	Change from Baseline
Sitting Systolic BP	mmII.a	High	≥ 180	Increase of ≥ 20
	mmHg	Low	≤ 90	Decrease of ≥ 20
Sitting Diastolic BP	mmII.a	High	≥ 105	Increase of ≥ 15
	mmHg	Low	≤ 50	Decrease of ≥ 15
Sitting Pulse rate	hom	High	≥ 120	Increase of ≥ 15
	bpm	Low	≤ 50	Decrease of ≥ 15
Waight	kg	High		Increase of $\geq 7\%$
Weight		Low		Decrease of ≥ 7%
Dagninatam, Data	hom	High	≥ 28	_
Respiratory Rate	bpm	Low	≤ 8	_
Tommoroturo	°C	High	> 38	_
Temperature		Low	< 35	_

BP = blood pressure; bpm = beats/breaths per minute

ECG values meeting *either* the actual value or change from baseline PCS high criteria will be categorized as PCS.

[figure not shown]
[figure not shown]

Table 8. Potentially Clinically Significant Criteria for ECG Parameters

[figure not shown]
Parameter		PCS High Criteria		
	Unit	Actual Value	Change from Baseline	
QRS interval	msec	≥ 150	_	
PR interval	msec	≥ 250	_	
QTcF	msec	> 500	Increase > 60	

QTcF = QTc Fridericia

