10.2. Appendix 2: Clinical Laboratory Tests

- The protocol-required tests detailed in Table 10-1 will be performed by the central laboratory.
- Nonprotocol-specified laboratory tests may be performed by the central laboratory or a local laboratory. The results from any local laboratory tests must be entered in the eCRF.
- Protocol-specific requirements for inclusion or exclusion of participants are detailed in Section 5.
- Additional tests may be performed at any time during the study as determined necessary by the investigator or required by local regulations.

Table 10-1 Protocol-required Safety Laboratory Assessments

Laboratory		Dan	
Assessments	D1 + 1 + + +		rameters
Hematology	Platelet count	RBC indices:	WBC count with differential (absolute):
	RBC count	MCV	Neutrophils
	Hemoglobin	MCH	Lymphocytes
	Hematocrit	MCHC	Monocytes
			Eosinophils
			Basophils
Clinical Chemistry ^a	BUN	Potassium	Aspartate aminotransferase (AST)
	Creatinine	Sodium	Alanine aminotransferase (ALT)
	Glucose (fastinge)	Calcium	Alkaline phosphatase
	Total protein	Cholesterol	Total, direct and indirect bilirubin
	Albumin	Chloride	
Routine Urinalysis	Specific gravity pH, glucose, protein, blood, ketones, bilirubin, urobilinogen, nitrite, leukocyte esterase		
dipstick		,	
	Microscopic examina	ation (if blood or prote	ein is abnormal)
Drugs of Abuse ^b	Benzoylecgonine (cocaine), methadone, barbiturates, amphetamines, benzodiazepines, alcohol ^c , cannabinoids, opiates, or phencyclidine at the Screening visit or Baseline		
Serology ^d	Hepatitis B surface antigen, anti-hepatitis C virus, and anti-human immunodeficiency virus type 1 and type 2		
Pregnancy test ^b	Serum β-hCG pregnancy test at Screening; serum or urine test on all other visits		
(WOCBP only)	1 2111 11 1 1 0 1	. 10.1 0	

^a In Stage 1, blood samples will be collected following 10-hour fasting period. In Stage 2, fasting will not be required.

Investigators must document their review of each laboratory safety report.

^b Urine dipstick kits may be used to conduct drugs of abuse and pregnancy tests; however, serum pregnancy test will be required at Screening

Breathalyzer may be used for alcohol

d For screening purposes only

^e Fasting requirement is for Stage 1 only

10.3. Appendix 3: Adverse Events: Definitions and Procedures for Recording, Evaluating, Follow-up, and Reporting

Definition of AE

AE Definition

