9.3 Analysis of Laboratory Data

Descriptive statistics for values and changes from the baseline in standard units at each assessment time point will be presented by study intervention group.

Clinical laboratory test values will be considered potentially clinically significant (PCS) if they meet either the lower-limit or upper-limit PCS criteria listed in Appendix C. The number and percentage of participants who have PCS post-baseline clinical laboratory values will be tabulated by study intervention for all scheduled postbaseline visit. The percentages will be calculated relative to the number of participants who have available non-PCS baseline values and at least 1 postbaseline assessment. The numerator will be the total number of participants with at least 1 PCS postbaseline value.

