6.3.6.1. Potentially Clinically Significant Criteria for Clinical Laboratory Parameters

Laboratory assessments values meeting any of the following PCS low or PCS high criteria will be categorized as PCS:

Table 6-5 Clinical Laboratory PCS Criteria

Laboratory Group	Parameter	SI Unit	PCS Low Limit	PCS High Limit
Hematology	Eosinophils absolute cell count	10 ⁹ /L	_	> 1.5 × ULN
	Hematocrit	%	< 0.8 × LLN	≥ 1.2 × ULN
	Hemoglobin	g/L	< 0.8 × LLN	≥ 1.2 × ULN
	Lymphocytes absolute cell count	10 ⁹ /L	< 0.8 × LLN	> 1.2 × ULN
	Neutrophils absolute cell count	10 ⁹ /L	< 0.6 × LLN	> 1.6 × ULN
	Platelet count (thrombocytes)	10 ⁹ /L	< 0.5 × LLN	> 1.5 × ULN
	Red blood cell count	$10^{12}/L$	< 0.8 × LLN	> 1.2 × ULN
	White blood cell count	10 ⁹ /L	< 0.7 × LLN	> 1.8 × ULN
Chemistry	Alanine aminotransferase	U/L	_	> 3 × ULN
	Albumin	g/L	< 0.9 × LLN	> 1.1 × ULN
	Alkaline phosphatase	U/L	_	> 3 × ULN
	Aspartate aminotransferase	U/L	_	> 3 × ULN
	Bilirubin, total	μmol/L	_	> 1.5 × ULN
	Blood urea nitrogen	mmol/L	_	> 1.3 × ULN
	Calcium	mmol/L	< 0.9 × LLN	> 1.1 × ULN
	Cholesterol, total	mmol/L	_	> 1.2 × ULN
	Creatinine	μmol/L	_	> 1.8 × ULN
	Glucose, fasting	mmol/L	< 0.8 × LLN	> 1.2 × ULN
	Glucose, nonfasting	mmol/L	< 0.8 × LLN	> 1.4 × ULN
	Phosphorus	mmol/L	< 0.8 × LLN	> 1.2 × ULN
	Potassium	mmol/L	< 0.9 × LLN	> 1.1 × ULN
	Protein, total	g/L	< 0.9 × LLN	> 1.1 × ULN
	Sodium	mmol/L	< 0.9 × LLN	> 1.1 × ULN
	Uric acid (urate)	μmol/L	_	> 1.2 × ULN
Urinalysis	Glucose	μmol/L	_	≥ 0.015
	Glucose (alternate units)	_	_	≥ 2+
	рН	_	< 0.9 × LLN	> 1.1 × ULN
	Protein	g/L		≥ 1.0
	Protein (alternate units)	_		≥ 2+
	Specific gravity			> 1.1 × ULN

Safety Statistical Analysis Plan

2012-201-005 [Stage 1]

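### Two urinalysis PCS limits do not work on their scales: urine glucose at 0.015 µmol/L catches any quantified result, and specific gravity above 1.1 × ULN catches none

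*SAP*

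**What the plan says.** Stage 2 SAP Appendix C, Table 6 has six urinalysis rows, and two matter here.

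- **Urine glucose.** The unit and high limit read "μmol/L ≥ 0.015". The next row, which begins "Glucose (alternate units", covers the same analyte and sets the limit at ≥ 2+.
- **Specific gravity.** The row reads "Specific gravity _ _ > 1.1 × ULN", with no low limit. The footnote says where the reference limit comes from: "ULN = upper limit of normal (value provided by the laboratory". Neither document gives a number for it.

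Stage 1 SAP section 6.3.6.1, Table 6-5 carries the same limits and the same glucose unit, under the rule "Laboratory assessments values meeting any of the following PCS low or PCS high criteria will be categorized as PCS".

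Stage 2 SAP section 9.3 turns the limits into a table by study intervention: "The numerator will be the total number of participants with at least 1 PCS postbaseline value". The denominator is restricted to participants who are not PCS at baseline and have a postbaseline assessment.

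Protocol Appendix 2, Table 10-1 describes routine urinalysis as a dipstick test whose analytes include "glucose, protein, blood, ketones, bilirubin, urobilinogen, nitrite, leukocyte esterase". Stage 1 SAP Table 5-6 also names the dipstick.

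**The concern.** A PCS limit is useful only if it falls inside the range of values the test can return, so that some results lie on each side of it. These two limits fall outside that range, at opposite ends.

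The numeric glucose limit is so low that it separates only zero from not zero. It also sits beside a ≥ 2+ limit for the same analyte that is plainly meant to catch marked glycosuria. The paired protein rows (≥ 1.0 g/L and ≥ 2+) show no such gap. The serum glucose rows use a different unit, as in "Glucose, nonfasting mmol/L", so µmol/L is not the table's usual unit for glucose.

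The specific gravity rule applies a percentage multiplier to a scale that starts at about 1.000 for water. A 10% margin on such a scale is much larger than it looks.

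Clinical laboratory values are part of the primary safety objective in both stages. Stage 2 SAP Appendix E removes between-group safety tests, so readers will rely on the descriptive counts. A row that must read 0% looks like reassurance although it could not have flagged anyone. A row that flags every quantified positive looks like a signal.

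**Working it through.** No stated figure needs reproducing, since the plan gives limits and not a calculation. The check is whether each limit lies in the range of possible results.

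**Inputs from the documents:** urine glucose limit 0.015 µmol/L; same analyte ≥ 2+ in alternate units; specific gravity limit 1.1 × ULN; ULN supplied by the laboratory.

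**Inputs not in the documents:** molar mass of glucose 180.16 g/mol and specific gravity of water 1.000 (constants); lowest measurable urine glucose 1 to 100 mg/dL, specific gravity ULN 1.020 to 1.040, and highest attainable urine specific gravity about 1.05 (assumptions).

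**Glucose: convert the limit**

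0.015 × 10⁻⁶ mol/L × 180.16 g/mol = 2.70 × 10⁻⁶ g/L = 2.7 µg/L = 0.00027 mg/dL.

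**Glucose: compare with what a test could report**

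- 1 mg/dL = 10 mg/L; 10 / 180.16 = 0.0555 mmol/L = 55.5 µmol/L; 55.5 / 0.015 ≈ 3,700.
- 100 mg/dL = 5,551 µmol/L; 5,551 / 0.015 ≈ 370,000.

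Across that whole range, the smallest quantified result is already thousands of times the limit.

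**Glucose: try other units for the same number**

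| Unit | 0.015 in that unit, as mg/dL |
|---|---|
| µmol/L (as written) | 0.00027 |
| mmol/L | 0.27 |
| mol/L | 270 |

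Only mol/L gives a size that could plausibly sit beside ≥ 2+. That suggests a unit slip but does not prove one.

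**Glucose: effect on the percentage**

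If concentrations are reported, any participant with quantified glucose at baseline is PCS at baseline and leaves the section 9.3 denominator. A later marked rise in that participant would then not appear in the rate, reading the numerator as a subset of the denominator.

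**Specific gravity: limit = 1.1 × ULN**

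| Assumed ULN | Limit |
|---|---|
| 1.000 (water, floor case) | 1.100 |
| 1.020 | 1.122 |
| 1.025 | 1.128 |
| 1.030 | 1.133 |
| 1.035 | 1.139 |
| 1.040 | 1.144 |

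For the limit to come down to 1.050, the ULN would have to be 1.050 / 1.1 = 0.955, which is below water. At a ULN of 1.030, a sample would need an excess over water of 0.133 against the ULN's 0.030, or 0.133 / 0.030 = 4.4 times as much. No ULN that a laboratory could supply for urine brings the limit into the assumed attainable range.

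**The case against.** The strongest reply is that the glucose row may never be used. Its companion is labelled as alternate units, so the two rows read as a choice that depends on how the laboratory reports. Testing is by dipstick, and no document says that a concentration is also reported. This stands. A reader might infer that a trace or 1+ result is PCS in one row and not in the other. The documents do not support that, because a graded result falls under the ≥ 2+ row alone. The numeric row does harm only if concentrations are reported.

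A reader might also infer that the urinalysis PCS rates as a whole carry no safety information. That goes too far. Glucose ≥ 2+, pH, and both protein rows are not in question, which is four of the six rows.

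The consequence is limited in other ways too. Investigators must document their review of each laboratory report (Protocol Appendix 2), and clinically relevant changes are recorded as adverse events (Protocol section 8.1.8). Stage 2 SAP section 9.3 also presents values and changes from baseline. No dose, stopping or monitoring committee rule in these documents depends on a PCS limit. Liver events have separate criteria. All of this stands and keeps the point minor.

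None of it rescues the specific gravity row, which fails whatever ULN is supplied. A PDF reading error is also unlikely, since both SAPs show the same limits and the same unit.

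**Conclusion.** The point holds as a minor error in two table rows.

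- **Specific gravity.** The row will read 0% in every arm. This does not depend on the laboratory's ULN: the limit exceeds 1.10 for any ULN above water, and the only assumption is that urine does not get there (ceiling taken as about 1.05).
- **Urine glucose.** The limit as written, 0.00027 mg/dL, is out of scale with the ≥ 2+ row. Whether it distorts a result is conditional: if concentrations are reported, it flags every quantified positive and removes participants with quantified glucose at baseline from the denominator; if only grades are reported, it is unused.

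It is tempting to state that the intended glucose unit was mol/L. The 270 mg/dL that this gives makes it likely, but nothing in the documents confirms it. The PCS tables are descriptive, and no efficacy result or planned test is affected.

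**What to change.** In the Stage 2 SAP, before final database lock:

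- **Urine glucose.** Ask the central laboratory how it reports the result and in what unit. Then correct the unit of the numeric row, or delete that row and use only ≥ 2+.
- **Specific gravity.** Drop the row, or replace the multiplier with an absolute limit on the laboratory's own scale, such as any value above its ULN. The second choice makes the row a plain out-of-range flag and will list some benign concentrated samples.

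The cost is one query to the laboratory, two table rows and the matching program lines.

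For Stage 1, section 10.0 of the Stage 2 SAP says that the data have already been locked, unmasked and analysed. New limits there would be chosen after unmasking. A documented note or correction is enough, saying that the specific gravity row could not flag anyone and whether the numeric glucose row was used.
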